7.2 Secondary Endpoints and the Analytical Methods

Analysis Set: Full Analysis Set

Analysis Variables:

- (1) Change of lipid component by Lipoprotein Fraction in Major Lipid
- (2) Change of fatty acid in all lipid and sd LDL-C
- (3) Change of serum lipid, lipid concentration of apolipoprotein and lipoprotein and particle number of lipoprotein

* See appendix 1 for detail of items.

Time Point: Week 0, Week 4, Week 8

Stratified Variable: Fasting Triglycerides (Week -4)

[Min ≤ - <300, 300 ≤ - <Max]

Age (Week -4) [Min ≤ - <65, 65 ≤ - <Max]

Analysis Methods: The same analyses described in 7.1 will be performed on the Items described above.

For the Analysis variable 2), exploratory analysis will be performed about relationship between percent change from baseline of sd LDL at Week 8 and percent change from baseline of fatty acid in all lipid at Week 8.

7.3 Other Analyses

Analysis Set: Full Analysis Set

Analysis Variables: Lipoprotein Lipase, HS-CRP

Time Point: Week 0, Week 4, Week 8

Analysis Methods: The same analyses described in 7.1(1), (2) will be performed on the Items described above.

8 SAFETY EVALUATION

8.1 Frequency of Adverse Event Occurrence

8.1.1 Brief Summary of Adverse Events

Analysis Set: Safety Analysis Set

Analysis Variables: Adverse Event(Treatment-Emergent Adverse Events),
Non-Serious TEAEs

Category Classification:

Causal relationship with treatment drug [Related, Not related]

Severity [Mild, Moderate, Severe]

Time to onset [1<= - <29, 29<= - <57, 57<= - <=Max]

For the above analysis items, the following analyses of frequency distribution will be performed.

- 1) All TEAEs
- 2) Drug-related TEAEs
- 3) All TEAEs by severity
- 4) Drug-related TEAEs by severity.
- 5) TEAEs leading to discontinuation
- 6) Serious TEAEs
- 7) Drug-related serious TEAEs
- 8) Serious TEAEs leading to discontinuation
- 9) TEAEs leading to death
- 10) TEAEs by time to onset

Incidence rates will be calculated as following on each analysis.

[Number of Subjects]

- Frequency by Severity

Subjects with one or more adverse events within a level of MedDRA term is counted only once in that level using the most severe incident. The denominator when calculating the incidence of adverse events is the number of subjects of safety analysis set.

- Frequency by Time to Onset

Subjects with one or more adverse events within a level of MedDRA term is counted in each period. The denominator when calculating the incidence of adverse events is the subject that “Drug continued after the period” or “TEAE was occurred after the period”. The numerator is the subject that “TEAE occurred in the period”.

- Analyses Other Than the Above

Subjects with one or more adverse events within a level of MedDRA term is counted only once for that MedDRA term. The denominator when calculating the incidence of adverse events is the number of subjects of safety analysis set.

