The duration of the treatment period is 8 weeks. Visit 1 is to obtain informed consent (Day -29 to Day -1 before the start of study drug administration), Visit 2 is to administer the study drug for the first time (Day -15 to Day -1 before the start of study drug administration), Visit 3 takes place in the 4th week after the start of study drug administration (Week 4), and Visit 4 is to administer the study drug for the last time (Week 8).

[2] Number of visits

Screening period: 1 visit

Treatment period: 3 visits

[figure not shown]
Figure 6 (a) shows an outline of the clinical study design. Refer to Appendix A for schedule of examinations, observations, and evaluations.

Figure 6.a Outline of the clinical study design

<Outline of the clinical study>

Duration of treatment: 8 weeks

Number of visits: 4 visits

(a) by HPLC

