10.2 Procedures

10.2.1 Collection and reporting of adverse events

10.2.1.1 Adverse event collection period

Adverse events shall be collected from the start of administration with the study drug until completion of the treatment period (or discontinuation).

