5 OTHER DATA HANDLING

[Data Handling for Study Drug]

- Duration of Treatment(Treated with Omega-3 FAE)

Duration of Treatment = Date of the Last Dose – Date of the First Dose + 1

[Data Handling for Duration of Hyperlipidemia]

- Duration of hyperlipidemia (year)

Duration of hyperlipidemia (year) = (Date of first dose (year/month) – Onset/Diagnosis

Date of hyperlipidemia (year/month)) / 12 (rounded off to two decimal places)

If only the month of the onset of hyperlipidemia is unknown, the month of the onset of hyperlipidemia is regarded as “January”.

[Data Handling for Below (or Above) the limit of Quantification]

- Efficacy Data

(Laboratory Test (except Total Cholesterol, TG, HDL-C) and Lipoprotein Fraction)

Below (or equal to) the limit of Quantification: Lower Limit of Quantification to be replaced.

Above (or equal to) the limit of Quantification: Upper Limit of Quantification to be replaced.

- Safety Data

(Vital Sign and Laboratory Test (Total Cholesterol, TG, HDL-C))

Below (or equal to) the limit of Quantification: 0 to be replaced.

Above (or equal to) the limit of Quantification: Upper Limit of Quantification to be replaced.

[Data Handling for Adverse Event]

- An adverse event is defined as any untoward medical occurrence in a patient or a subject receiving a pharmaceutical product (including the study drug). It does not necessarily have an apparent causal relationship with this pharmaceutical product (including study drug). A treatment-emergent AE (TEAE) is defined as an AE which occurs after taking the first dose of trial medication.
The first dose date of “Not treated with Omega-3 FAE” is defined as the next day of the visit in Week 0.
- Time to first Onset
Time to first Onset=AE Start date - The first dose date + 1
- Related AE
AE is classified into Related/Not Related only for Treated with Omega-3 FAE group
- Non-Serious TEAEs
Non-Serious TEAE is defined as Non-Serious TEAEs of at least 5% in any treatment group by SOC and PT.

[Laboratory Test]

- (EPA+DHA)/AA Ratio
(Eicosapentaenoic Acid + Docosahexaenoic Acid)/ Arachidonic Acid
- DHA/AA Ratio
Docosahexaenoic Acid / Arachidonic Acid
- non-HDL
Total Cholesterol - HDL-C

6 SUBJECTS, DEMOGRAPHIC and OTHER BASELINE CHARACTERISTICS

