6.1 Subject Disposition

6.1.1 Study Information

Analysis Set: All subjects who were obtained informed consent

Analysis Variables: The earliest date of informed consent

The latest date of the last date of administration

MedDRA Version

SAS Version

Analysis Methods: For the above analysis items, the following analysis will be performed.

- (1) Show the above items.

The latest date of the last date of administration will be presented only for treated with Omega-3 FAE.

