6.3.3 Study Medication Exposure

Analysis Set: Safety Analysis Set

Analysis Variables: Duration of exposure (days),

[1<= - <29, 29<= - <57, 57<= - <=Max]

Analysis Methods: For the above analysis items, the following analysis will be performed for each treatment group and all subjects in the analysis set.

- (1) Summary of frequency distribution for categorical variables and summary statistics for continuous variables

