8.1.2 Display of TEAE

Analysis Set: Safety Analysis Set

Analysis Variables: TEAE

Category Classification:

Relationship with treatment drug [Related, Not Related]

Severity [Mild, Moderate, Severe]

Time to onset [1<= - <29, 29<= - <57, 57<= - <=Max]

Analysis Methods: For the above analysis items, the following analysis will be performed for each treatment group. Analysis variables will be coded using the MedDRA dictionary and be summarized into SOC and PT. SOC's will be sorted in alphabetical order, then PTs will be sorted in frequency order.

- 1) All TEAEs by SOC and PT
- 2) Drug-related TEAEs by SOC and PT
- 3) All TEAEs by severity by SOC and PT
- 4) Drug-related TEAEs by severity by SOC and PT
- 5) TEAEs leading to discontinuation by SOC and PT
- 6) Serious TEAEs by SOC and PT
- 7) Non-serious TEAEs of at least 5% in any group by SOC and PT
- 8) Drug-related serious TEAEs by SOC and PT
- 9) Serious TEAEs leading to discontinuation by SOC and PT
- 10) TEAEs leading to death
- 11) TEAEs by time to onset, SOC and PT.

Incidence rates will be calculated as following on each analysis.

[Number of Subjects]

- Frequency (by SOC/PT)

Within each summary, subjects with one or more adverse events within a level of SOC term is counted only once in that level. Similarly, subjects with one or more adverse events within a level of PT term is counted only once in that level. The denominator when calculating the incidence of adverse events is the number of subjects of safety analysis set.

- Frequency by Severity (by SOC/PT)

Subjects with one or more adverse events within a level of SOC/PT term is counted only once in that level using the most severe incident. The denominator when calculating the incidence of adverse events is the

number of subjects of safety analysis set.

- Frequency by Time to Onset

Subjects with one or more adverse events within a level of MedDRA term is counted in each period. The denominator when calculating the incidence of adverse events is the subject that “Drug continued after the period” or “TEAE was occurred after the period”. The numerator is the subject that “TEAE occurred in the period”.

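### The time-to-onset adverse event denominator, as written, leaves out subjects who finish within the period (unless they have a later event), is zero from Day 57 on, and has no end date for controls

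*SAP*

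**What the plan says.** - **Rule.** For onset by period (SAP 8.1.1 item 10, SAP 8.1.2 item 11), the denominator "is the subject that “Drug continued after the period” or “TEAE was occurred after the period". On the other side, "The numerator is the subject that “TEAE occurred in the period". The wording is the same in both sections.
- **Periods.** Days 1 to below 29, 29 to below 57, and 57 to Max.
- **Planned course.** Treatment lasts 8 weeks, and Protocol 6.1 states "Visit 4 is to administer the study drug for the last time (Week 8". Protocol Appendix A sets the Visit 4 window at Days 42 to 70, and SAP section 2 sets the Week 8 reference at Day 56.
- **Control dates.** SAP section 5 gives controls a surrogate first dose date, which "is defined as the next day of the visit in Week 0". The only duration rule in that section is labelled "Duration of Treatment(Treated with Omega-3 FAE". SAP 6.1.1 adds: "The latest date of the last date of administration will be presented only for treated with Omega-3 FAE". SAP 6.3.3 nevertheless tabulates "Duration of exposure (days" for each treatment group.
- **Collection period.** Protocol 10.2.1.1 collects adverse events from the start of study drug "until completion of the treatment period (or discontinuation". The SAP rule does not refer to that date.

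**The concern.** A rate for a period should divide the subjects with an event in the period by those at risk in it, so every numerator subject should also be in the denominator. This rule counts the denominator after the period is over. Subjects who have an event and stop in the same period, whom an onset table most needs to count properly, can fall out of their own denominator. So can completers who finish on schedule. For controls, the condition about drug continuing has no value at all.

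Protocol 13.1.4 asks for adverse event frequency by time of onset for each treatment group. If the rule is programmed as written, omega-3 period rates can be overstated or undefined, and control rates cannot be computed until someone chooses an end date.

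**Working it through.** The plan gives no figure for this rule, so there is none to reproduce. The check is a direct count.

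**1. The rule in symbols.** For a period from day *a* to day *b*, let *L* be a subject's last day on drug and *T* any TEAE onset day.

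- Numerator: some *T* with *a* ≤ *T* ≤ *b*.
- Denominator as written: *L* > *b*, or some *T* > *b*.
- Denominator counted from the start of the period: *L* ≥ *a*, or some *T* ≥ *a*.

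A TEAE with *a* ≤ *T* ≤ *b* always satisfies *T* ≥ *a*, so under the third rule the numerator lies inside the denominator. It never satisfies *T* > *b*, so under the written rule it need not.

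**2. Last period.** With *b* = Max, nothing can exceed *b*. The written denominator is 0 whatever the data.

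**3. Planned completion.** 8 weeks × 7 = 56 days, so an on-schedule subject treated from Day 1 ends on Day 56, the last day of the second period. Then *L* > 56 is false, and the subject leaves the Days 29-56 denominator unless a later TEAE is recorded. Adverse event collection stops at completion or discontinuation, so that will seldom happen. The Visit 4 window spans 70 − 42 + 1 = 29 days, of which 14 (Days 57-70) lie beyond Day 56. If last doses were spread evenly over it (an assumption), about 25 × 14/29 ≈ 12 of 25 subjects (48%) would remain in the denominator.

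**4. Worked example, omega-3 arm only.** The arm size of 25 is the planned number (Protocol 13.3). All event and last-dose days are assumed. TEAEs start on Days 5, 10, 14, 18 and 24, on Days 33, 40 and 50, and on Day 58, each in a different subject. The subject with the Day 18 event stops on Day 20. The other 24 continue to Day 60.

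| Period | As written | From start of period |
|---|---|---|
| Days 1-28 | 5/24 = 20.8% | 5/25 = 20.0% |
| Days 29-56 | 3/24 = 12.5% | 3/24 = 12.5% |
| Days 57-Max | 1/0, undefined | 1/24 = 4.2% |

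**5. Completers ending on Day 56.** Let *k* of the 24 end on Day 56, with the Day 58 subject among those followed to Day 60. The written Days 29-56 denominator is 24 − *k*; counted from the start of the period it stays at 24.

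| *k* | As written | From start of period |
|---|---|---|
| 6 | 3/18 = 16.7% | 3/24 = 12.5% |
| 12 | 3/12 = 25.0% | 3/24 = 12.5% |
| 18 | 3/6 = 50.0% | 3/24 = 12.5% |
| 24, Day 58 event removed | 3/0, undefined | 3/24 = 12.5% |

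In the last row both rules give 0 for Days 57-Max. Counted from the start of the period, that 0 is legitimate, because nobody is at risk after Day 56 and the numerator is also 0.

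**6. Controls.** *L* is not defined, because these subjects take no study drug. SAP section 5 fixes their Day 1 and nothing fixes their last day. No control percentage can be computed under either rule.

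**The case against.** The best defence is that the wording is loose English for in or after the period. The clause that adds subjects with a TEAE looks designed to keep numerator subjects in the denominator, and it does so only on that reading. A rule that gives zero for the last period on any data is unlikely to be what was meant. This is plausible, and it would remove every omega-3 discrepancy above. But the SAP does not say it, and version 2 revised both 8.1.1 and 8.1.2 without listing a change to this rule. It also supplies no end date for controls. The by-group exposure table in SAP 6.3.3 suggests that a surrogate is intended, but none is stated.

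Other points stand as limits:

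- The example uses assumed data. A period rate is unchanged when nobody finishes within that period, as the 12.5% against 12.5% in the first table shows.
- A subject who finishes within a period but has a later TEAE stays in the denominator.
- Protocol 13.1.4 asks for a tabulation and names no denominator, so counts by period could still be shown for both arms.
- Protocol 10.2.1.1 does not say whether discontinuation means stopping the drug or leaving the study.

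**Conclusion.** The rule is wrong as written and should be changed. It can exclude numerator subjects from the denominator, it gives zero for Days 57-Max, and it removes on-schedule completers from Days 29-56. In the example the Days 29-56 rate runs from the correct 12.5% up to 50.0%, and is undefined when all completers end on Day 56. Those sizes rest on the literal reading and on assumed event and last-dose days. The missing control end date does not depend on either.

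The effect is limited to period rates in two descriptive safety tables. Numerator counts, overall TEAE rates and efficacy results do not depend on this rule.

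**What to change.** In SAP 8.1.1 and 8.1.2, define the denominator as subjects still under adverse event observation, or with a TEAE, on or after the first day of the period. Add one sentence that ends observation in both arms at the completion or discontinuation date, in line with Protocol 10.2.1.1, with control Day 1 the day after the Week 0 visit. State whether discontinuation refers to drug or study, and give the date to be used in each arm. Moving from drug continuation to observation changes the omega-3 at-risk definition slightly, but it gives both arms the same basis.

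The cost is one phrase and one sentence in two sections, plus minor programming. The visit windows in SAP section 2 already need visit dates; that a discontinuation date is recorded is assumed here and should be confirmed against the CRF.

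A separate and broader point is that the Safety Analysis Set in SAP section 3 requires a dose of study drug. Taken literally, that excludes controls from every safety table. One sentence stating that randomized controls are included would settle it.

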8.1.2 Display of TEAE

Analysis Set: Safety Analysis Set

Analysis Variables: TEAE

Category Classification:

Relationship with treatment drug [Related, Not Related]

Severity [Mild, Moderate, Severe]

Time to onset [1<= - <29, 29<= - <57, 57<= - <=Max]

Analysis Methods: For the above analysis items, the following analysis will be performed for each treatment group. Analysis variables will be coded using the MedDRA dictionary and be summarized into SOC and PT. SOC's will be sorted in alphabetical order, then PTs will be sorted in frequency order.

- 1) All TEAEs by SOC and PT
- 2) Drug-related TEAEs by SOC and PT
- 3) All TEAEs by severity by SOC and PT
- 4) Drug-related TEAEs by severity by SOC and PT
- 5) TEAEs leading to discontinuation by SOC and PT
- 6) Serious TEAEs by SOC and PT
- 7) Non-serious TEAEs of at least 5% in any group by SOC and PT
- 8) Drug-related serious TEAEs by SOC and PT
- 9) Serious TEAEs leading to discontinuation by SOC and PT
- 10) TEAEs leading to death
- 11) TEAEs by time to onset, SOC and PT.

Incidence rates will be calculated as following on each analysis.

[Number of Subjects]

- Frequency (by SOC/PT)

Within each summary, subjects with one or more adverse events within a level of SOC term is counted only once in that level. Similarly, subjects with one or more adverse events within a level of PT term is counted only once in that level. The denominator when calculating the incidence of adverse events is the number of subjects of safety analysis set.

- Frequency by Severity (by SOC/PT)

Subjects with one or more adverse events within a level of SOC/PT term is counted only once in that level using the most severe incident. The denominator when calculating the incidence of adverse events is the

number of subjects of safety analysis set.

- Frequency by Time to Onset

Subjects with one or more adverse events within a level of MedDRA term is counted in each period. The denominator when calculating the incidence of adverse events is the subject that “Drug continued after the period” or “TEAE was occurred after the period”. The numerator is the subject that “TEAE occurred in the period”.

8.2 Vital Signs and Laboratory Test

8.2.1 Vital Signs

Analysis Set: Safety Analysis Set

Analysis Variables: Sitting blood pressure (Systolic, Diastolic), Sitting Pulse (bpm)

Time Point: Week 0, Week 4, Week 8

Analysis Methods: For the above analysis items, the following analysis will be performed

- (1) Summary statistics for observed value will be calculated by Time point.

Line plot of individual data will also be provided.

- (2) The same analyses described in (1) will be performed on change (Week4 /8 –Week 0) from baseline.

8.2.2 Laboratory Test

Analysis Set: Safety Analysis Set

Analysis Variables: Hematology (Platelets)

Serum Chemistry(Total Cholesterol, TG, HDL-C, non-HDL ,
LDH, AST, ALT, ALP, γ -GTP, CK(CPK))

Category Classification: Classification by reference value

[Lower, Normal, High]

Time Point: Week 0, Week 4, Week 8

Analysis Methods: For the above analysis items, the following analysis will be performed

- (1) Summary statistics for observed value will be calculated by time point.

Line plot of individual data will also be provided.

- (2) The same analyses described in (1) will be performed on change (Week4 /8 –Week 0) from baseline.

- (3) Shift table will be reported by time point with classification above.

9 LISTING

Following lists will be create for randomized subjects

- Demographics
- Medical history
- Concurrent medical conditions
- Medication history
- Concomitant medications
- Compliance of drug exposure
- Discontinued subjects
- Vital Signs
- Laboratory Test (Lipoprotein fraction)
- Laboratory Test (Hematology, Serum chemistry)
- Laboratory Test (Apoprotein, Remnant lipoprotein)
- Laboratory Test (Fatty acid analysis of total serum lipids)
- Adverse Events

10 CONSIDERATIONS on STATISTICAL ANALYSIS

10.1 Adjustments for Covariates

ANCOVA will be performed on primary and secondary endpoints with Fasting triglycerides at week -4($\text{Min} \leq - < 300$, $300 \leq - \leq \text{Max}$), and Age at week -4($\text{Min} \leq - < 65$, $65 \leq \text{Max}$) as covariate. Details are described in 7.1(5) and 7.2.

10.2 Handling of Dropouts or Missing Data

Imputation will not be performed.

10.3 Criteria for Interim Analysis and Early Discontinuation

Interim analysis will not be performed.

10.4 Multicenter Studies

Analyses for consideration of centers will not be performed.

10.5 Multiple Comparisons/Multiplicity

It does not adjust multiplicity.

10.6 Subgroup Analysis

Subgroup analysis will be performed in 7.1 and 7.2.

11 REVISION HISTORY

Ver.	Date	Author	Revised Content	Reason for Revision
1	30NOV2016	PPD	First Edition	
2	31OCT2017	PPD	5.OTHER DATA HANDLING [Data Handling for Adverse Event] “Non-Serious TEAEs” and “Laboratory Test”	Additional items
			6.1.3.1.Status at the End of Study Analysis Variables: (Before) Status at the End of Study Drug (After) Status at the End of Study Analysis Methods: (Before) For the above analysis items, the following analysis will be performed only for Treated with Omega-3 FAE (After) For the above analysis items, the following analysis will be performed for each treatment group and all subjects in the analysis set.	Correction of errors

Ver.	Date	Author	Revised Content	Reason for Revision
			8.1.1.Brief Summary of Adverse Events Analysis Variables: (Before) Adverse Events (Treatment-Emergent Adverse Events) (After) Adverse Events (Treatment-Emergent Adverse Events), Non-Serious TEAEs	Additional items
			8.1.2.Display of TEAE Non-serious TEAEs of at least 5% in any group by SOC and PT	Additional items
			8.2.1.Vital Signs (3) Shift table, by using classification based on criteria, will be made at each time point (Week 4 or Week 8) from Week 0	Deleted the section in terms of meaning of Vital Signs in this Study
			8.2.2.Laboratory Test Analysis Variables: (Before) Serum Chemistry (LDH, AST, ALT, ALP, γ -GTP, CK(CPK)) (After) Serum Chemistry(Total Cholesterol, TG, HDL-C, non-HDL , LDH, AST, ALT, ALP, γ -GTP, CK((CPK))	Correction of errors
			Category Classification: Classification by reference value [Lower, Normal, High]	Additional items

Appendix 1 Details of Analysis Variables

Primary Efficacy Endpoint and Secondary Efficacy Endpoint in Protocol are described below in detail.

1. Efficacy Analysis

1.1 Primary Endpoint

1) Change of sd LDL-C by Lipoprotein fraction and particle size of LDL

(1) sd LDL-C by Lipoprotein Fraction

Cholesterol Concentration in sd LDL Fraction

Triglycerides Concentration in sd LDL Fraction

Free Cholesterol Concentration in sd LDL Fraction

Phospholipid Concentration in sd LDL Fraction

TG/Cholesterol ratio in sd LDL Fraction

(2) Particle Size of LDL

Particle Size of LDL (Cholesterol Monitor)

Particle Size of LDL (Triglycerides Monitor)

Particle Size of LDL (Free Cholesterol Monitor)

Particle Size of LDL (Phospholipid Monitor)

